Enrolled participants were randomly divided into probiotics group or placebo group. Seventeen and 19 participants were respectively assigned to the placebo group and the probiotics group. The probiotics we used were in the form of 100mg L. bulgaricus powder packets, each containing 1×10^8 CFU of probiotics (TCI CO., Taipei, Taiwan). Initially (day 1), participants underwent measurements for weight, body fat, and BMI, and fasting blood

[figure not shown]
IRB/REC No. :	CMUH110-REC2-070
Page No. :	5/28

samples were collected. Subsequently, each participant received one package of either probiotic or a placebo sample, along with drinking water on the same day. From that point onward, participants self-administered one package of the sample daily for 12 weeks and the participants' sample consumption and physical conditions were tracked by the research assistants weekly. Throughout the study duration, participants maintained their regular diet and lifestyle. At the endpoint (day 84), weight, body fat, and BMI were measured, and fasting blood samples were collected again. Weight and body fat were measured with Karada Scan 216 (OMRON, Kyoto, Japan). Alanine aminotransferase (ALT), aspartate aminotransferase (AST), blood urea nitrogen (BUN), creatinine (CRE), CHOL, HDL-C, LDL-C, TG, hemoglobin A1c (HbA1c), and Glucose-Ante Cibum (Glu-AC) levels were analyzed and reported by Laboratory Medicine in Chinese Medical University Hospital (Taichung, Taiwan). Data were expressed as the mean \pm standard error of the mean (SEM). Statistical significance between groups were done by student paired t-test or Mann-Whitney test. P-values lower than 0.05 were considered statistically significant.

Data Analysis:

The statistical analysis was conducted using GraphPad's unpaired independent samples t-test, with significance set at $*P < 0.05$.

Flow Diagram of the study:

Group	Placebo		Probiotics	
	Mean	SD	Mean	SD
Age, years	41.38	12.71	41.56	10.92
Gender, male/female	7/6		12/6	
Weight, kg	78.69	15.64	80.77	15.11
Body fat, %	32.08	6.65	30.84	5.26
BMI	29.32	5.40	28.89	3.59
ALT, U/L	26.00	15.37	32.63	18.96
AST, U/L	21.45	10.62	23.36	7.44
BUN, mg/dL	13.10	2.69	13.67	2.94
CRE, mg/dL	0.80	0.14	0.83	0.15
CHOL, mg/dL	182.18	43.04	201.60	40.97
HDL-C, mg/dL	46.82	5.82	48.50	16.26
LDL-C, mg/dL	122.82	42.15	111.01	30.40
TG, mg/dL	139.62	52.18	220.94	173.92
HbA1c, %	5.80	0.83	6.17	1.07
Glu-AC, mg/dL	93.45	16.92	109.06	34.13

Table 1: Analysis of Baseline Values of the Participants

Results

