Placebo represents the placebo control group, and Probiotics represents the probiotics experimental group. Individual comparisons of changes in lipids carried by serum lipoproteins before and after sample consumption are depicted. The size of the points in the scatter plot ($-\log_{10}$ p values) and the color (log2 fold change denoted as log2FC, with red indicating positive correlation changes and blue indicating negative correlation changes) are used to distinguish between inter-group differences and trends. Serum very low-density lipoprotein (VLDL), low-density lipoprotein (LDL), and high-density lipoprotein (HDL) have the ability to carry cholesterol (Chol), lipids, cholesterol esters (CE), and triglycerides (TG) individually. The experimental data indicate that probiotics upregulate the content of

IRB/REC No. :	CMUH110-REC2-070
Page No. :	13/28

lipids carried by HDL (Chol:Lipid and CE:Lipid). Simultaneously, there is a significant decrease in the total amount of lipids carried by VLDL (L-VLDL, XL-VLDL, XXL-VLDL). Additionally, there is a significant decrease in triglycerides (TG) carried by both VLDL and HDL.

IRB/REC No. :	CMUH110-REC2-070
Page No. :	14/28

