Appendix

Figure 5: Extracted Meaningful Components from Metabolomic Analysis Results, Other Results Provided in the Appendix °

Table 3: List of Name Abbreviations and Units

Excel column name	Biomarker name	Unit
Total-C	Total cholesterol	mmol/l
non-HDL-C	Total cholesterol minus HDL-C	mmol/l
Remnant-C	Remnant cholesterol (non-HDL, non-LDL -cholesterol)	mmol/l
VLDL-C	VLDL cholesterol	mmol/l
Clinical LDL-C	Clinical LDL cholesterol	mmol/l
LDL-C	LDL cholesterol	mmol/l
HDL-C	HDL cholesterol	mmol/l
Total-TG	Total triglycerides	mmol/l
VLDL-TG	Triglycerides in VLDL	mmol/l
LDL-TG	Triglycerides in LDL	mmol/l
HDL-TG	Triglycerides in HDL	mmol/l
Total-PL	Total phospholipids in lipoprotein particles	mmol/l
VLDL-PL	Phospholipids in VLDL	mmol/l
LDL-PL	Phospholipids in LDL	mmol/l
HDL-PL	Phospholipids in HDL	mmol/l
Total-CE	Total esterified cholesterol	mmol/l
VLDL-CE	Cholesteryl esters in VLDL	mmol/l
LDL-CE	Cholesteryl esters in LDL	mmol/l
HDL-CE	Cholesteryl esters in HDL	mmol/l
Total-FC	Total free cholesterol	mmol/l
VLDL-FC	Free cholesterol in VLDL	mmol/l
LDL-FC	Free cholesterol in LDL	mmol/l
HDL-FC	Free cholesterol in HDL	mmol/l
Total-L	Total lipids in lipoprotein particles	mmol/l
VLDL-L	Total lipids in VLDL	mmol/l
LDL-L	Total lipids in LDL	mmol/l
HDL-L	Total lipids in HDL	mmol/l
Total-P	Total concentration of lipoprotein particles	mmol/l
VLDL-P	Concentration of VLDL particles	mmol/l
LDL-P	Concentration of LDL particles	mmol/l
HDL-P	Concentration of HDL particles	mmol/l
VLDL size	Average diameter for VLDL particles	nm
LDL size	Average diameter for LDL particles	nm
HDL size	Average diameter for HDL particles	nm
Phosphoglyc	Phosphoglycerides	mmol/l

IRB/REC No. :	CMUH110-REC2-070
Page No. :	15/28

TG/PG	Ratio of triglycerides to phosphoglycerides	ratio
Cholines	Total cholines	mmol/l
Phosphatidylc	Phosphatidylcholines	mmol/l
Sphingomyelins	Sphingomyelins	mmol/l
ApoB	Apolipoprotein B	g/l
ApoA1	Apolipoprotein A1	g/l
ApoB/ApoA1	Ratio of apolipoprotein B to apolipoprotein A1	ratio
Total-FA	Total fatty acids	mmol/l
Unsaturation	Degree of unsaturation	degree
Omega-3	Omega-3 fatty acids	mmol/l
Omega-6	Omega-6 fatty acids	mmol/l
PUFA	Polyunsaturated fatty acids	mmol/l
MUFA	Monounsaturated fatty acids	mmol/l
SFA	Saturated fatty acids	mmol/l
LA	Linoleic acid	mmol/l
DHA	Docosahexaenoic acid	mmol/l
Omega-3 %	Ratio of omega-3 fatty acids to total fatty acids	%
Omega-6 %	Ratio of omega-6 fatty acids to total fatty acids	%

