PUFA %	Ratio of polyunsaturated fatty acids to total fatty acids	%
MUFA %	Ratio of monounsaturated fatty acids to total fatty acids	%
SFA %	Ratio of saturated fatty acids to total fatty acids	%
LA %	Ratio of linoleic acid to total fatty acids	%
DHA %	Ratio of docosahexaenoic acid to total fatty acids	%
PUFA/MUFA	Ratio of polyunsaturated fatty acids to monounsaturated fatty acids	ratio
Omega-6/Omega-3	Ratio of omega-6 fatty acids to omega-3 fatty acids	ratio
Ala	Alanine	mmol/l
Gln	Glutamine	mmol/l
Gly	Glycine	mmol/l
His	Histidine	mmol/l
Total BCAA	Total concentration of branched-chain amino acids (leucine + isoleucine + valine)	mmol/l
Ile	Isoleucine	mmol/l
Leu	Leucine	mmol/l
Val	Valine	mmol/l
Phe	Phenylalanine	mmol/l
Tyr	Tyrosine	mmol/l
Glucose	Glucose	mmol/l
Lactate	Lactate	mmol/l
Pyruvate	Pyruvate	mmol/l
Citrate	Citrate	mmol/l
Glycerol	Glycerol	mmol/l
βOHbutyrate	3-Hydroxybutyrate	mmol/l
Acetate	Acetate	mmol/l
Acetoacetate	Acetoacetate	mmol/l
Acetone	Acetone	mmol/l
Creatinine	Creatinine	μ mol/l

IRB/REC No. :	CMUH110-REC2-070
Page No. :	16/28

Albumin	Albumin	g/l
GlycA	Glycoprotein acetyls	mmol/l
XXL-VLDL-P	Concentration of chylomicrons and extremely large VLDL particles	mmol/l
XXL-VLDL-L	Total lipids in chylomicrons and extremely large VLDL	mmol/l
XXL-VLDL-PL	Phospholipids in chylomicrons and extremely large VLDL	mmol/l
XXL-VLDL-C	Cholesterol in chylomicrons and extremely large VLDL	mmol/l
XXL-VLDL-CE	Cholesteryl esters in chylomicrons and extremely large VLDL	mmol/l
XXL-VLDL-FC	Free cholesterol in chylomicrons and extremely large VLDL	mmol/l
XXL-VLDL-TG	Triglycerides in chylomicrons and extremely large VLDL	mmol/l
XL-VLDL-P	Concentration of very large VLDL particles	mmol/l
XL-VLDL-L	Total lipids in very large VLDL	mmol/l
XL-VLDL-PL	Phospholipids in very large VLDL	mmol/l
XL-VLDL-C	Cholesterol in very large VLDL	mmol/l
XL-VLDL-CE	Cholesteryl esters in very large VLDL	mmol/l
XL-VLDL-FC	Free cholesterol in very large VLDL	mmol/l
XL-VLDL-TG	Triglycerides in very large VLDL	mmol/l
L-VLDL-P	Concentration of large VLDL particles	mmol/l
L-VLDL-L	Total lipids in large VLDL	mmol/l
L-VLDL-PL	Phospholipids in large VLDL	mmol/l
L-VLDL-C	Cholesterol in large VLDL	mmol/l
L-VLDL-CE	Cholesteryl esters in large VLDL	mmol/l
L-VLDL-FC	Free cholesterol in large VLDL	mmol/l
L-VLDL-TG	Triglycerides in large VLDL	mmol/l
M-VLDL-P	Concentration of medium VLDL particles	mmol/l
M-VLDL-L	Total lipids in medium VLDL	mmol/l
M-VLDL-PL	Phospholipids in medium VLDL	mmol/l

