no	XXL_VLDL_P	0	0	t-test	0.992	-0.012	0.01	0.002
no	XXL_VLDL_PL	0.026	0.026	t-test	0.986	-0.021	0.017	0.002
no	XXL_VLDL_PL_pct	14.889	16.636	t-test	1.117	0.16	0.527	0.06
no	XXL_VLDL_TG	0.084	0.074	t-test	0.879	-0.187	0.136	0.01
no	XXL_VLDL_TG_pct	34.697	43.814	t-test	1.263	0.337	0.413	0.06

IRB/REC No. :	CMUH110-REC2-070
Page No. :	25/28

Table 5: Comparative Analysis of Metabolomic Pre-test and Post-test Results for Probiotics Group Blood Samples

Differential expression analysis								
Significance(p-value)	Feature	Mean(after)	Mean(before)	Method	FC	Log2(FC)	-Log10(p-value)	-Log10(padj)
yes	Acetate	0.017	0.019	t-test	1.156	0.209	1.329	0.407
yes	Gly	0.263	0.295	t-test	1.123	0.167	1.447	0.407
yes	HDL_size	9.573	9.508	t-test	0.993	-0.01	1.433	0.407
yes	Lactate	4.175	5.984	t-test	1.433	0.519	1.441	0.407
yes	L_VLDL_CE_pct	14.036	15.354	t-test	1.094	0.129	1.363	0.407
yes	L_VLDL_C_pct	28.119	29.999	t-test	1.067	0.093	1.505	0.407
yes	L_VLDL_FC_pct	14.083	14.645	t-test	1.04	0.056	1.643	0.421
yes	L_VLDL_L	0.563	0.48	t-test	0.853	-0.229	1.334	0.407
yes	L_VLDL_TG	0.288	0.233	t-test	0.81	-0.304	2.037	0.533
yes	L_VLDL_TG_pct	51.128	49.056	t-test	0.959	-0.06	1.429	0.407
yes	M_HDL_CE_pct	37.7	39.269	t-test	1.042	0.059	2.902	0.805
yes	M_HDL_C_pct	46.11	47.515	t-test	1.03	0.043	3.121	0.805
yes	M_HDL_PL_pct	47.018	46.34	t-test	0.986	-0.021	1.977	0.533
yes	M_HDL_TG_pct	6.873	6.145	t-test	0.894	-0.161	1.715	0.463
yes	M_VLDL_PL_pct	21.414	22.043	t-test	1.029	0.042	1.319	0.407
yes	S_HDL_CE_pct	27.533	28.901	t-test	1.05	0.07	1.987	0.533
yes	S_HDL_C_pct	37.973	39.337	t-test	1.036	0.051	2.162	0.533
yes	S_HDL_PL_pct	55.964	55.036	t-test	0.983	-0.024	1.839	0.52
yes	S_HDL_TG_pct	6.063	5.628	t-test	0.928	-0.107	1.571	0.407
yes	S_LDL_C_pct	62.862	63.718	t-test	1.014	0.019	2.566	0.645
yes	TG_by_PG	0.778	0.696	t-test	0.895	-0.161	1.792	0.508
yes	VLDL_size	39.666	39.173	t-test	0.988	-0.018	2.006	0.533
yes	VLDL_TG	1.623	1.384	t-test	0.853	-0.229	1.355	0.407
yes	XL_HDL_CE_pct	36.249	38.447	t-test	1.061	0.085	1.922	0.524
yes	XL_HDL_C_pct	52.182	56.422	t-test	1.081	0.113	1.345	0.407
yes	XL_VLDL_L	0.381	0.323	t-test	0.847	-0.239	1.334	0.407
yes	XL_VLDL_TG	0.221	0.181	t-test	0.818	-0.291	1.843	0.52
yes	XXL_VLDL_L	0.467	0.375	t-test	0.804	-0.315	1.494	0.407
yes	XXL_VLDL_P	0	0	t-test	0.817	-0.292	1.395	0.407
yes	XXL_VLDL_TG	0.267	0.202	t-test	0.756	-0.403	2.073	0.533
no	Acetoacetate	0.026	0.017	t-test	0.651	-0.619	0.697	0.243
no	Acetone	0.016	0.02	t-test	1.238	0.308	0.6	0.219

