no	S_HDL_PL	0.727	0.72	t-test	0.991	-0.013	0.079	0.026
no	S_HDL_TG	0.082	0.08	t-test	0.967	-0.049	0.238	0.1
no	S_LDL_C	0.225	0.232	t-test	1.035	0.05	0.388	0.158
no	S_LDL_CE	0.173	0.178	t-test	1.026	0.037	0.24	0.1
no	S_LDL_CE_pct	48.121	48.302	t-test	1.004	0.005	0.188	0.073
no	S_LDL_FC	0.051	0.055	t-test	1.067	0.093	1.031	0.384
no	S_LDL_FC_pct	14.741	15.416	t-test	1.046	0.065	0.854	0.308
no	S_LDL_L	0.358	0.365	t-test	1.021	0.029	0.212	0.081
no	S_LDL_P	0	0	t-test	1.021	0.03	0.194	0.074
no	S_LDL_PL	0.106	0.107	t-test	1.009	0.012	0.089	0.027
no	S_LDL_PL_pct	29.648	29.377	t-test	0.991	-0.013	0.371	0.158
no	S_LDL_TG	0.028	0.026	t-test	0.948	-0.076	0.358	0.158
no	S_LDL_TG_pct	7.49	6.906	t-test	0.922	-0.117	0.774	0.274
no	Sphingomyelins	0.477	0.472	t-test	0.989	-0.015	0.088	0.027
no	S_VLDL_C	0.199	0.206	t-test	1.033	0.047	0.162	0.057
no	S_VLDL_CE	0.126	0.131	t-test	1.04	0.056	0.193	0.074
no	S_VLDL_CE_pct	21.368	22.914	t-test	1.072	0.101	1.147	0.407
no	S_VLDL_C_pct	33.978	36.404	t-test	1.071	0.1	1.189	0.407
no	S_VLDL_FC	0.073	0.074	t-test	1.022	0.031	0.105	0.03
no	S_VLDL_FC_pct	12.61	13.49	t-test	1.07	0.097	1.238	0.407
no	S_VLDL_L	0.61	0.595	t-test	0.975	-0.037	0.123	0.039

IRB/REC No. :	CMUH110-REC2-070
Page No. :	28/28

no	S_VLDL_P	0	0	t-test	0.966	-0.05	0.165	0.057
no	S_VLDL_PL	0.133	0.133	t-test	0.998	-0.003	0.008	0.004
no	S_VLDL_PL_pct	22.398	23.208	t-test	1.036	0.051	1.163	0.407
no	S_VLDL_TG	0.279	0.257	t-test	0.922	-0.117	0.453	0.179
no	S_VLDL_TG_pct	43.624	40.388	t-test	0.926	-0.111	1.19	0.407
no	Total_BCAA	0.486	0.521	t-test	1.071	0.099	0.842	0.308
no	Total_C	5.128	5.17	t-test	1.008	0.012	0.07	0.024
no	Total_CE	3.693	3.734	t-test	1.011	0.016	0.1	0.028
no	Total_FA	16.38	15.438	t-test	0.943	-0.085	0.618	0.22
no	Total_FC	1.435	1.436	t-test	1.001	0.001	0.005	0.003
no	Total_L	10.668	10.37	t-test	0.972	-0.041	0.248	0.103
no	Total_P	0.018	0.018	t-test	0.999	-0.001	0.008	0.004
no	Total_PL	3.313	3.224	t-test	0.973	-0.039	0.239	0.1
no	Total_TG	2.227	1.976	t-test	0.887	-0.172	1.011	0.384
no	Tyr	0.066	0.07	t-test	1.046	0.065	0.448	0.177
no	Unsaturation	1.369	1.37	t-test	1	0.001	0.018	0.004
no	Val	0.272	0.288	t-test	1.06	0.084	0.657	0.227
no	VLDL_C	0.929	0.909	t-test	0.978	-0.031	0.107	0.03
no	VLDL_CE	0.523	0.526	t-test	1.004	0.006	0.02	0.004
no	VLDL_FC	0.406	0.383	t-test	0.945	-0.082	0.314	0.139
no	VLDL_L	3.254	2.949	t-test	0.906	-0.142	0.708	0.245
no	VLDL_P	0	0	t-test	0.958	-0.063	0.261	0.111
no	VLDL_PL	0.702	0.655	t-test	0.934	-0.099	0.411	0.159

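### The Figure 5 text reports a significant fall in the lipid carried by VLDL on the strength of three subclasses, and does not say that the panel's own VLDL total is not significant (P = 0.20)

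*Combined protocol and SAP*

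**What the plan says.** The text below Figure 5 (Results) describes changes in the probiotics arm and states: "Simultaneously, there is a significant decrease in the total amount of lipids carried by VLDL (L-VLDL, XL-VLDL, XXL-VLDL"). No P-value accompanies the sentence, and the VLDL total is not mentioned.

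The rule for significance is in Methods and Design, under Study Design and Intervention: "P-values lower than 0.05 were considered statistically significant". No rule for multiplicity is given.

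Table 3 (Appendix) defines VLDL-L as "Total lipids in VLDL" and XXL-VLDL-L as "Total lipids in chylomicrons and extremely large VLDL".

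Table 5 (Appendix) gives the within-arm pre/post results for the probiotics group. The whole-class row reads "no VLDL_L 3.254 2.949 t-test 0.906 -0.142 0.708 0.245", where the leading word is the significance flag and the last two figures are −log10 of the raw and adjusted P. A row for one of the named subclasses reads "yes L_VLDL_L 0.563 0.48 t-test 0.853 -0.229 1.334 0.407".

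**The concern.** The quantity that the sentence appears to describe, all the lipid carried by VLDL, has its own row in the panel, and that row is flagged as not significant. The sentence rests instead on three of six subclasses, which are exactly the three flagged as significant. A reader who does not turn to the VLDL_L row in the appendix will take away a whole-class fall.

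This matters because the texts for Figures 1 to 4 report no significant difference between the groups on body composition, blood sugar, blood lipids, or liver and kidney function. The Figure 5 text therefore carries much of what is favourable in the report, and its wording should match its own table.

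**Working it through.** **Inputs.** All rows are from Table 5 (probiotics arm). The threshold is P < 0.05, which is −log10 P > 1.301.

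**The printed row reproduces.** The fold change is the second mean column divided by the first: 2.949 / 3.254 = 0.906, and log2(0.906) = −0.142. Both match the VLDL_L row.

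**P-values.** P = 10^(−printed value), for example 10^(−0.708) = 0.196.

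| Row | First mean | Second mean | −log10 P | Raw P | −log10 adj. P | Adjusted P | Flag |
|---|---|---|---|---|---|---|---|
| VLDL_L (total) | 3.254 | 2.949 | 0.708 | 0.196 | 0.245 | 0.57 | no |
| XXL_VLDL_L | 0.467 | 0.375 | 1.494 | 0.032 | 0.407 | 0.39 | yes |
| XL_VLDL_L | 0.381 | 0.323 | 1.334 | 0.046 | 0.407 | 0.39 | yes |
| L_VLDL_L | 0.563 | 0.480 | 1.334 | 0.046 | 0.407 | 0.39 | yes |
| M_VLDL_L | 0.816 | 0.762 | 0.434 | 0.368 | 0.172 | 0.67 | no |
| S_VLDL_L | 0.610 | 0.595 | 0.123 | 0.753 | 0.039 | 0.91 | no |
| XS_VLDL_L | 0.417 | 0.414 | 0.045 | 0.902 | 0.009 | 0.98 | no |

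Rounding of the printed value puts the raw P for VLDL_L between 0.1957 and 0.1961.

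**VLDL_L is the sum of the six subclasses.**
- First column: 0.467 + 0.381 + 0.563 + 0.816 + 0.610 + 0.417 = 3.254.
- Second column: 0.375 + 0.323 + 0.480 + 0.762 + 0.595 + 0.414 = 2.949.

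Both sums equal the printed totals. The total already contains the three named subclasses, XXL included, and is still not significant.

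**Weight of the subclasses.**
- M + S + XS = 0.816 + 0.610 + 0.417 = 1.843, and 1.843 / 3.254 = 57% of VLDL lipid. In the second column the share is 1.771 / 2.949 = 60%.
- L + XL + XXL goes from 1.411 to 1.178, a difference of 0.233. The difference in the total is 3.254 − 2.949 = 0.305.

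**Other whole-class rows in Table 5.**
- VLDL_TG: 10^(−1.355) = 0.044, flagged yes (adjusted P = 10^(−0.407) = 0.39).
- VLDL_P: 10^(−0.261) = 0.55, flagged no.
- VLDL_C: 10^(−0.107) = 0.78, flagged no.
- HDL_TG: 10^(−0.361) = 0.44, flagged no.

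**Direction.** The first mean column is headed as the after value and the second as the before value. As printed, VLDL_L and the three named subclasses therefore rise. Table 2 points the other way. There, probiotics TG falls (220.9 to 199.9 mg/dL) and LDL-C rises (113.0 to 119.0 mg/dL). In Table 5, Total_TG (2.227 after, 1.976 before) and Clinical_LDL_C (2.854 after, 3 before) show the opposite under the printed headings. A swap of the headings would explain this, but the documents do not settle it. The P-values do not depend on it.

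**The case against.** The strongest reply is that the parenthesis limits the claim. In Table 3 the suffix L stands for all lipid species within a class, so the sentence can be read as total lipid in each of the three named subclasses. The sentence before it also uses a parenthesis to say which features are meant. On that reading it lists exactly the VLDL lipid rows flagged yes, and it agrees with the table and the raw threshold. The appendix also says that Figure 5 shows a selection, and the VLDL_L row is printed there for anyone to check. This much stands: the fault is wording that is too general and leaves out the negative total. A reader might infer that the table flatly contradicts the sentence or that the result was invented; the documents do not support that.

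Four other inferences also go too far.

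- *That VLDL shows no signal at all.* Whole-class VLDL_TG is flagged yes (P = 0.044). Non-significance in a small arm is also not evidence of no change: the M difference (0.054) is nearly as large as the XL difference (0.058), and the three named classes supply 0.233 of the 0.305 mmol/L difference in the total.
- *That the XXL change reflects recent meals, because Table 3 puts chylomicrons in that class.* The Methods state that blood was taken fasting at both visits, and nothing in the documents points to a meal effect.
- *That XXL should not be counted as VLDL.* The panel's own total includes XXL in full, so VLDL_L cannot be relied on while XXL is set aside.
- *That the table shows smaller VLDL particles or lower lipid in the large classes.* Under the printed headings these values are higher after treatment.

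The reply does not remove the main point. The sentence can still be read as a statement about the class as a whole, and it does not disclose that the class total was tested and was not significant.

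**Conclusion.** The point holds as a fault of over-general wording. A significant change in total VLDL lipid is not supported: VLDL_L has raw P = 0.20, about four times the stated threshold, and adjusted P = 0.57. What Table 5 supports is narrower: nominal, unadjusted, within-arm differences in L, XL and XXL (P = 0.046, 0.046 and 0.032), none of which passes on the table's adjusted P (0.39 each). M, S and XS, with 57% of VLDL lipid, are not significant.

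This rests on the printed P-values. The tests cannot be rerun, because Table 5 gives no standard deviations or individual data. The conclusion on significance is the same whichever way the before and after columns are read; any statement of direction is not. The sentence concerns an exploratory panel and not the weight outcome, so the change is one that should be made to a stated conclusion, without bearing on the main result.

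**What to change.** Reword the sentence below Figure 5 to say that total VLDL lipids (VLDL-L) did not change significantly within the probiotics arm (P = 0.20), and that nominal, unadjusted, within-arm differences were seen only in the L, XL and XXL subclasses.

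Alongside it:
- list all six subclasses with their raw and adjusted P-values;
- label the XXL row as Table 3 does, "Total lipids in chylomicrons and extremely large VLDL";
- support any statement on totals with the whole-class rows, both favourable and not: VLDL_L (P = 0.20), VLDL_TG (P = 0.044) and, for the following sentence on triglycerides, HDL_TG (P = 0.44);
- reconcile the before and after headings of Tables 4 and 5 against the source data and Table 2 before stating any direction or fold change.

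The cost is one reworded sentence, a short list drawn from rows already printed, and a check of the column headings. No new data or analysis is needed. The stated result becomes less favourable.

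### In Tables 4 and 5 the column headings and the fold change contradict each other, so the tables as headed reverse the directions stated in the Figure 5 legend

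*Combined protocol and SAP*

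**What the plan says.** The Figure 5 legend (Results) makes three directional statements about the probiotics arm. Lipids carried by HDL, expressed as cholesterol and cholesteryl ester relative to total lipid, went up. For VLDL, "there is a significant decrease in the total amount of lipids carried by VLDL (L-VLDL, XL-VLDL, XXL-VLDL"). Triglycerides carried by VLDL and HDL also went down. The figure's points are coloured by log2 fold change.

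The supporting numbers are in the Appendix. Table 5 is titled "Comparative Analysis of Metabolomic Pre-test and Post-test Results for Probiotics Group Blood Samples", and Table 4 is its placebo counterpart. Both carry the headings "Mean(after) Mean(before) Method FC Log2(FC"), so the first mean is labelled as the later visit and the second as the earlier one. Probiotics rows include:

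- "L_VLDL_L 0.563 0.48 t-test 0.853 -0.229 1.334 0.407"
- "XL_VLDL_L 0.381 0.323 t-test 0.847 -0.239 1.334 0.407"
- "XXL_VLDL_L 0.467 0.375 t-test 0.804 -0.315 1.494 0.407"
- "XXL_VLDL_TG 0.267 0.202 t-test 0.756 -0.403"
- "Total_TG 2.227 1.976 t-test 0.887"

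The document nowhere defines which visit is the numerator of FC.

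**The concern.** In each of those rows the mean headed as after is the larger one, yet FC is below 1 and, where quoted, its logarithm is negative. A reader who trusts the headings concludes that these lipids rose on the product. A reader who trusts FC, or the legend, concludes that they fell.

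The report finds no significant between-group difference in body composition, blood sugar, blood lipids, or liver and kidney function. The Figure 5 statements are therefore its main positive finding on the product, and their sign depends on which label is right.

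**Working it through.** **Step 1: which ratio gives the printed FC?** Inputs are the printed means in Tables 4 and 5, allowing for three-decimal rounding.

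| Row | Before/after as headed | Printed FC | After/before as headed |
|---|---|---|---|
| L_VLDL_L, probiotics | 0.480/0.563 = 0.853 | 0.853 | 1.173 (+17.3%) |
| XL_VLDL_L, probiotics | 0.323/0.381 = 0.848 | 0.847 | 1.180 (+18.0%) |
| XXL_VLDL_L, probiotics | 0.375/0.467 = 0.803 | 0.804 | 1.245 (+24.5%) |
| VLDL_TG, probiotics | 1.384/1.623 = 0.853 | 0.853 | 1.173 (+17.3%) |
| XXL_VLDL_TG, probiotics | 0.202/0.267 = 0.757 | 0.756 | 1.322 (+32.2%) |
| M_HDL_TG_pct, probiotics | 6.145/6.873 = 0.894 | 0.894 | 1.118 (+11.8%) |
| M_HDL_C_pct, probiotics | 47.515/46.11 = 1.030 | 1.03 | 0.970 (-3.0%) |
| M_HDL_CE_pct, probiotics | 39.269/37.7 = 1.042 | 1.042 | 0.960 (-4.0%) |
| Creatinine, placebo | 59.285/64.21 = 0.923 | 0.923 | 1.083 (+8.3%) |

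The same check covered 38 rows of Table 5 (29 of the 30 flagged rows) and 15 rows of Table 4 (all 8 flagged). Before/after reproduces the printed FC in 38 of 38 and 15 of 15; after/before does so in none. Rows whose means print as 0, such as XXL_VLDL_P, cannot be checked. The pattern is systematic, so a stray typing error does not explain it.

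**Step 2: which element is wrong?** Table 2 gives hospital means before and after treatment. If the headings are transposed, the printed FC is a true after/before ratio and should move the same way as post/pre in Table 2.

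| Analyte | Probiotics, Table 2 post/pre | Printed FC | Placebo, Table 2 post/pre | Printed FC |
|---|---|---|---|---|
| TG | 199.9/220.9 = 0.905 | 0.887 | 177.4/139.6 = 1.271 | 1.022 |
| LDL-C (clinical) | 119.0/113.0 = 1.053 | 1.051 | 112.4/122.8 = 0.915 | 0.933 |
| Total cholesterol | 204.6/200.7 = 1.019 | 1.008 | 186.3/186.9 = 0.997 | 0.946 |
| HDL-C | 47.38/48.55 = 0.976 | 0.978 | 46.43/46.82 = 0.992 | 0.930 |
| Glucose | 100.7/109.3 = 0.921 | 0.890 | 91.69/91.77 = 0.999 | 0.883 |
| Creatinine | 0.8775/0.8241 = 1.065 | 0.949 | 0.7915/0.7962 = 0.994 | 0.923 |

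Eleven of 12 directions agree with the printed FC. The exception is probiotic creatinine: the hospital ratio is 1.065, and the table as headed gives 72.354/68.671 = 1.054.

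**Step 3: how firm is 11 of 12?** Probiotic TG and LDL-C in both arms are the informative agreements. Placebo cholesterol, glucose and creatinine move by less than 1% in the hospital data, so their direction says little. Probiotic glucose is unreliable: the Table 2 means differ by 100.7 - 109.3 = -8.6 mg/dL, but the printed change is +1.389. Taking that change instead would make it a second exception.

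**The case against.** The strongest reply is that this is probably a heading slip, repeated in two appendix tables. If so, FC, log2FC and the legend's directions are all correct, and the repair is two header cells per table. Table 2 supports that view, and calling the hospital data evenly split would understate it. The creatinine exception is weak, being non-significant in both sources (p = 0.0535 in Table 2; 10^-0.784 = 0.16 in Table 5). The Figure 3 legend adds that 65% of probiotic participants had a fall in TG, against 18% on placebo.

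This part of the reply stands: transposed headings are the likelier explanation. It does not remove the defect. If the headings are transposed, the before and after means are mislabelled throughout both tables; if they are right, the legend is wrong. One or the other has to be corrected.

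A reader might infer from the tables as headed that probiotics raised VLDL lipids, and so did harm. The documents do not support that. It is the less likely reading on the hospital data, and no Table 5 row reaches 0.05 after the table's own adjustment: the smallest adjusted p is 10^-0.805 = 0.157, and the three VLDL lipid rows quoted above are at 10^-0.407 = 0.39. Neither direction is established on that basis. The body composition and Table 2 results are not affected by this point.

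**Conclusion.** The contradiction is real and systematic. Read as headed, Table 5 shows rises of 17% to 25% in the three VLDL lipid measures and VLDL triglycerides, and 32% in XXL-VLDL triglycerides. Read with the headings exchanged, the printed FC gives falls of 15% to 20% and 24%. The HDL statements reverse in the same way.

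The documents favour exchanged headings but cannot settle it. That preference assumes that the metabolomic and hospital values come from the same participants and visits, which the Methods text does not state for the metabolomic samples. It also rests on group means, which need not cover the same people at both visits. The directional statements should not be relied on until the source data have been checked.

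**What to change.** 1. Check the visit codes in the metabolomic source file, and state in the Methods and both table captions that FC is day 84 divided by day 1.
2. Compare direction participant by participant with the hospital TG, LDL-C, total cholesterol and creatinine values.
3. If the headings are transposed, correct them in Tables 4 and 5. FC, log2FC, Figure 5 and the legend's directions then stand.
4. If the headings are right, invert FC and log2FC in both tables, regenerate Figure 5 and reverse the legend's directional statements.
5. Hold those statements until step 1 or 2 has confirmed which case applies.

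The cost is a short data check and corrected headings or regenerated tables. It needs no new samples and no change to trial conduct.

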no	Ala	0.373	0.401	t-test	1.074	0.103	0.738	0.264
no	Albumin	41.766	43.735	t-test	1.047	0.066	1.025	0.384
no	ApoA1	1.521	1.487	t-test	0.978	-0.032	0.18	0.068
no	ApoB	1.001	1.016	t-test	1.015	0.021	0.123	0.039
no	ApoB_by_ApoA1	0.669	0.698	t-test	1.044	0.062	0.667	0.227
no	boHbutyrate	0.074	0.09	t-test	1.218	0.284	0.375	0.158
no	Cholines	2.989	2.88	t-test	0.963	-0.054	0.368	0.158
no	Citrate	0.062	0.062	t-test	1.012	0.017	0.143	0.052
no	Clinical_LDL_C	2.854	3	t-test	1.051	0.072	0.548	0.211
no	Creatinine	72.354	68.671	t-test	0.949	-0.075	0.784	0.275
no	DHA	0.287	0.269	t-test	0.94	-0.09	0.163	0.057
no	DHA_pct	1.763	1.862	t-test	1.056	0.079	0.258	0.111
no	Gln	0.546	0.549	t-test	1.006	0.009	0.072	0.024
no	Glucose	4.989	4.441	t-test	0.89	-0.168	0.66	0.227
no	GlycA	0.94	0.938	t-test	0.998	-0.003	0.029	0.004
no	Glycerol	0.099	0.119	t-test	1.202	0.265	0.326	0.144
no	HDL_C	1.29	1.262	t-test	0.978	-0.032	0.151	0.054
no	HDL_CE	0.986	0.971	t-test	0.985	-0.022	0.103	0.029
no	HDL_FC	0.303	0.291	t-test	0.957	-0.063	0.324	0.144
no	HDL_L	3.102	2.984	t-test	0.962	-0.056	0.286	0.122
no	HDL_P	0.016	0.016	t-test	0.997	-0.004	0.021	0.004
no	HDL_PL	1.592	1.515	t-test	0.952	-0.071	0.39	0.158
no	HDL_TG	0.22	0.208	t-test	0.942	-0.085	0.361	0.158

IRB/REC No. :	CMUH110-REC2 -070
Page No. :	26/28

no	His	0.075	0.083 t-test	1.115	0.157	0.962	0.364
no	IDL_C	0.867	0.864 t-test	0.997	-0.004	0.022	0.004
no	IDL_CE	0.654	0.648 t-test	0.991	-0.013	0.086	0.027
no	IDL_CE_pct	49.557	49.108 t-test	0.991	-0.013	0.588	0.219
no	IDL_C_pct	65.567	65.379 t-test	0.997	-0.004	0.198	0.074
no	IDL_FC	0.212	0.216 t-test	1.018	0.025	0.156	0.057
no	IDL_FC_pct	16.01	16.271 t-test	1.016	0.023	0.405	0.158
no	IDL_L	1.321	1.326 t-test	1.004	0.006	0.036	0.004
no	IDL_P	0	0 t-test	0.96	-0.059	0.352	0.158
no	IDL_PL	0.305	0.313 t-test	1.026	0.036	0.298	0.127
no	IDL_PL_pct	23.096	23.591 t-test	1.021	0.031	0.914	0.337
no	IDL_TG	0.149	0.149 t-test	0.998	-0.003	0.013	0.004
no	IDL_TG_pct	11.338	11.03 t-test	0.973	-0.04	0.297	0.127
no	Ile	0.072	0.076 t-test	1.053	0.074	0.458	0.179
no	LA	5.312	5.015 t-test	0.944	-0.083	0.6	0.219
no	LA_pct	33.147	34.014 t-test	1.026	0.037	0.435	0.172
no	LDL_C	2.043	2.135 t-test	1.045	0.064	0.627	0.222
no	LDL_CE	1.542	1.603 t-test	1.039	0.055	0.518	0.189
no	LDL_FC	0.5	0.532 t-test	1.064	0.09	0.967	0.364
no	LDL_L	2.992	3.111 t-test	1.04	0.056	0.496	0.184
no	LDL_P	0.001	0.001 t-test	1.035	0.05	0.367	0.158
no	LDL_PL	0.714	0.741 t-test	1.037	0.052	0.43	0.172

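### The Figure 5 legend reports a significant fall in HDL triglycerides, but Table 5 shows no significant change in any HDL triglyceride concentration

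*Combined protocol and SAP*

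**What the plan says.** The legend to Figure 5 (Results) makes statements about lipoprotein lipids in the probiotics group. Two concern HDL.

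- On HDL lipid, the sentence opens "The experimental data indicate that probiotics upregulate the content of" and continues after a page break with "lipids carried by HDL (Chol:Lipid and CE:Lipid". It does not use the word significant, and its parenthesis names two ratios to total lipid.
- On triglycerides, the legend says "there is a significant decrease in triglycerides (TG) carried by both VLDL and HDL". This sentence has no ratio qualifier.

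The criterion is set under Study Design and Intervention: "P-values lower than 0.05 were considered statistically significant". Table 3 in the Appendix defines HDL-TG as "Triglycerides in HDL" in mmol/l, a concentration, and lists the percentage measures (for example S-HDL-TG %) separately as ratios to total lipids.

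Table 5 in the Appendix gives the within-arm before/after tests for the probiotics group. Its HDL triglyceride row reads "HDL_TG 0.22 0.208 t-test 0.942 -0.085 0.361 0.158" and is flagged no. Its HDL total lipid row begins "HDL_L 3.102 2.984 t-test 0.962" and is also flagged no.

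**The concern.** The legend claims significance for a quantity that its own table marks as non-significant. The legends to Figures 1 to 4 all report no significant difference between groups, so Figure 5 is the only figure legend that claims a significant effect. A reader who takes it at face value would believe that the product lowers the triglyceride carried by HDL. The companion sentence could lead the same reader to think that HDL carries more lipid, when the flagged rows describe a shift in composition.

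**Working it through.** **Inputs.** Table 5 prints -log10(p), -log10(padj), two means and FC. The threshold p < 0.05 corresponds to -log10(p) > 1.301. I convert with p = 10^(-x), where x is the printed value.

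**HDL triglyceride concentrations**

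| Row | x | p | Flag |
|---|---|---|---|
| HDL_TG | 0.361 | 0.436 | no |
| XL_HDL_TG | 0.376 | 0.421 | no |
| L_HDL_TG | 0.359 | 0.438 | no |
| M_HDL_TG | 0.427 | 0.374 | no |
| S_HDL_TG | 0.238 | 0.578 | no |

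None of the five reaches 0.05.

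**HDL triglyceride as a share of lipid**

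| Row | x | p | padj | Flag |
|---|---|---|---|---|
| M_HDL_TG_pct | 1.715 | 0.019 | 10^(-0.463) = 0.344 | yes |
| S_HDL_TG_pct | 1.571 | 0.027 | 10^(-0.407) = 0.392 | yes |
| L_HDL_TG_pct | 0.027 | 0.940 | 10^(-0.004) = 0.991 | no |
| XL_HDL_TG_pct | 0.015 | 0.966 | 10^(-0.004) = 0.991 | no |

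**VLDL half of the same sentence.** VLDL_TG: 10^(-1.355) = 0.044. L, XL and XXL: 10^(-2.037) = 0.009, 10^(-1.843) = 0.014, 10^(-2.073) = 0.008. These are concentrations and all are flagged yes.

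**HDL lipid amounts.** HDL_L: 10^(-0.286) = 0.518. HDL_C: 10^(-0.151) = 0.706. HDL_CE: 10^(-0.103) = 0.789. All are flagged no.

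**All HDL rows.** There are 35 HDL concentration rows (30 lipid, 5 particle). None is below 0.05; the smallest p is 10^(-1.022) = 0.095, for XL_HDL_PL. Ten of the 20 HDL percentage rows are flagged yes: C, CE, PL and TG in M and in S, and C and CE in XL. HDL_size is also flagged (10^(-1.433) = 0.037).

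**Adjusted p.** The largest -log10(padj) anywhere in Table 5 is 0.805, so the smallest adjusted p is 10^(-0.805) = 0.157. The padj column agrees with Benjamini-Hochberg over 250 features at ranks 2 and 3 (0.805 and 0.645, as printed).

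**Direction.** FC equals Mean(before)/Mean(after) as the columns are headed. For M_HDL_C_pct, 47.515/46.11 = 1.030; for M_HDL_TG_pct, 6.145/6.873 = 0.894; for HDL_L, 2.984/3.102 = 0.962; each is the printed FC. Read literally, M_HDL_C_pct fell (47.515 to 46.11), M_HDL_TG_pct rose (6.145 to 6.873) and HDL_TG rose (0.208 to 0.220). These are the opposite of the legend. With the headers swapped, the legend's directions fit, but then HDL_L falls (3.102 to 2.984). On neither reading does total HDL lipid rise while HDL triglyceride falls.

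Table 2 lets one compare the sign of change for triglycerides, total cholesterol, LDL-C (against Clinical_LDL_C), HDL-C, creatinine and glucose. In the placebo group (Table 4, same headers) all six fit a swap. In the probiotics group five of six do, using the Pre and Post means; creatinine is the exception. Probiotics glucose also moves to the other side if the Change row (+1.389) is used instead of the means (109.3 to 100.7). This makes a swap likely but does not prove it.

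**The case against.** The strongest reply is that the authors meant composition throughout. The HDL lipid sentence says so in its parenthesis, does not claim significance, and names the ratios that are flagged: C% and CE% in M, S and XL HDL. Testing that sentence against HDL_L, HDL_C and HDL_CE tests something the parenthesis excludes. This largely stands. What remains is that speaking of content describes a shift in shares as if it were an amount.

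The triglyceride sentence may simply have lost the same qualifier, and Figure 5, whose labels might settle it, is not available in the text reviewed. That may explain the wording but does not rescue it. The authors marked ratios where they meant them, Table 3 separates the two measures, and the VLDL half of the sentence is nominally true for concentrations, so the HDL half will be read the same way. Even as percentages, only two of four subclasses are flagged.

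It can also be said that these features lie outside the stated goal of body weight and obesity-related risk factors, that the report finds no between-group difference in blood lipids (HDL-C change p = 0.9872 in Table 2), and that every concentration row is printed. This limits the harm but does not make the sentence correct.

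**Conclusion.** The claim of a significant decrease in HDL triglycerides is wrong as written: none of five concentrations is significant, with p from 0.374 to 0.578. It should be corrected. The HDL lipid sentence is a lesser fault of description.

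A reader might infer more than the documents support:

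- That the whole triglyceride sentence fails. It does not; the VLDL half has unadjusted support.
- That the HDL lipid sentence is a second flat contradiction. It makes no claim of significance and names the ratios that are flagged.
- That only percentages are flagged among HDL features. This is true of lipid measures, but HDL_size is flagged too.
- That HDL triglycerides actually rose. This follows from the printed headers alone, which are themselves in doubt, and the change is non-significant either way.

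The conclusion rests on Table 5's printed p-values and on reading the unqualified phrase as a concentration, as Table 3 defines it. It does not depend on which way the headers are resolved. All these tests are within-arm, so neither the flagged nor the unflagged rows establish a difference from placebo, and non-significance does not show that nothing changed.

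**What to change.** 1. Check the source data and reconcile the Mean(after) and Mean(before) headers of Table 5 with the FC column and the legend. Check Table 4, which has the same headers. Until this is done, no direction should be stated for any row.
2. Remove the claim of a significant HDL triglyceride decrease. State that HDL total lipid, HDL-C, HDL-CE and HDL-TG concentrations did not change significantly.
3. Reword the HDL lipid sentence as a composition result. Name the flagged percentages (C% and CE% in M, S and XL HDL; TG% and PL% in M and S HDL) with the reconciled direction, raw and adjusted p, and the matching concentrations alongside.
4. Label these results, and the VLDL results kept in the legend, as exploratory within-arm findings, and say that no Table 5 row is significant after adjustment (smallest padj 0.157).

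The cost is the header check and a few sentences. No new data or analysis is needed. The downside is a weaker claim.
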